Appendix 2: Criteria for discharge from hospital

Discharge Criteria Applied on Days 1, 8 and 15

On Days 1, 8 and 15, at Visit P1 and at the visit during which the transition from TP2 to TP3 took place, ECG and SBP/DBP were monitored for up to 6 hours post-dose. At the time of discharge (i.e., 6-hour post-dose) must have been met:

- HR >50 bpm, and SBP >90 mmHg
- No ECG abnormality or AE requiring continued hospitalization or prohibiting study continuation as an out-patient

If a patient did not meet the discharge criteria (as described above) at 6 hours post-dose, the patient was carefully monitored for an additional period, and a 12-lead ECG and a BP measurement was performed every 2 hours. The patient was kept in hospital for observation until changes in ECG/BP parameters were regarded as no longer being clinically relevant.

Study drug was permanently discontinued if the patient did not meet the criteria for discharge at 12 hours post-dose.

Discharge Criteria Applied for Study Drug Re-initiation

Discharge from post-dose monitoring on the first day of re-initiation of study drug following drug interruptions, can occur at the earliest when the evaluation of the pre-dose and all the hourly (± 15 minutes) post-dose ECGs until 4 hours post-dose have been obtained, provided the following criteria have been met:

- ECG-derived resting HR >45 bpm, and if HR <50 bpm it must not be the lowest value post-dose;
- SBP >90 mmHg;
- QT corrected for HR on the basis of Fridericia's formula (QTcF) <500 ms and QTcF increase from pre-dose <60 ms;
- No persisting significant ECG abnormality (e.g., AV block second or third degree) or ongoing AE requiring continued hospitalization or prohibiting study continuation as an out-patient.

If the patient does not meet the discharge criteria (as described above) at 4-hour post-dose, the patient should be carefully monitored for an additional period of up to 8 hours, and a 12-lead ECG and a BP measurement must be performed every hour. The patient can be discharged from post-dose monitoring as soon as the above criteria are met.

Should the patient not meet the criteria for discharge from post-dose monitoring at 12-hour post-dose, she/he must be permanently discontinued from study drug. Patients who are permanently discontinued should not be discharged from post-dose monitoring before vital signs return to near baseline values or until there is no persisting ECG abnormality

Ponesimod / ACT-128800 / JNJ-67896153		EudraCT 2009-011470-15
Multiple Sclerosis		EDMS-ERI-206617631
Protocol AC-058B202	Confidential	
Version 12		
15 March 2022, page 146/179		

(e.g., AV block second degree or higher), ongoing AE requiring continued cardiac monitoring, or until medically indicated.

Ponesimod / ACT-128800 / JNJ-67896153 Multiple Sclerosis Protocol AC-058B202 Version 12 15 March 2022, page 147/179

Confidential

EudraCT 2009-011470-15 EDMS-ERI-206617631

For patients with prior exposure to natalizumab or other immunosuppressive agents who have been enrolled in the study and who, under the study treatment, present new neurological symptoms suggestive of pathology other than MS, the investigator should consider PML or another opportunistic infection of the CNS and, in case of clinical features indicative of these conditions, the following diagnostic procedures are recommended:

Ponesimod / ACT-128800 / JNJ-67896153 Multiple Sclerosis		EudraCT 2009-011470-15 EDMS-ERI-206617631
Protocol AC-058B202	Confidential	
Version 12		
15 March 2022, page 148/179		

- Perform MRI including T1 sequences with gadolinium and include comparison with the previous MRI images in the interpretation of the MRI results. NB: In addition, fluid-attenuated inversion recovery (FLAIR) and diffusion-weighted imaging (DWI) sequences may be performed and sent to MIAC. MIAC will only analyze the additional sequences selected by the local radiologist, neuroradiologist, or neurologist with MRI expertise, upon notification for review of the investigational site. In that instance, MIAC will communicate the results of the review to the site.
- Interrupt study drug until PML or other opportunistic CNS infections has been excluded with confidence.
- Perform lumbar puncture and send cerebrospinal fluid (CSF) for JCV DNA testing by polymerase chain reaction (PCR) with an ultrasensitive assay. The JCV DNA assay should be based on quantitative real-time PCR to maximize sensitivity and specificity for detection, and an assay with a maximum lower limit of quantification of 50 DNA copies per mL should be used.

Detection of JCV DNA in the CSF of a symptomatic patient confirms the diagnosis. However, a negative JCV PCR result should not exclude a possible diagnosis of PML.

If the CSF is negative but clinical signs and symptoms and/or MRI are still suggestive of PML:

- Consider repeating CSF analysis
- Consider other opportunistic infections with CNS manifestations
- Manage the patient on suspicion of PML or other opportunistic CNS infections according to local guidelines

If

- There are no suspicious signs of PML or other opportunistic infections on MRI; and
- Lumbar puncture, if done, is negative for JCV DNA; and
- The neurological signs and symptoms show improvement and are no longer suspicious of PML and can be explained by MS or an alternative, not-infectious etiology,

other causes of the atypical neurological signs or symptoms or MRI findings need to be considered. Re-starting of the study drug should be considered if the benefit risk is still favorable, according to the investigator.

However, if the investigator is still NOT able to rule out PML or another CNS opportunistic infection the study drug should be permanently discontinued, the case should be reported

Ponesimod / ACT-128800 / JNJ-67896153 Multiple Sclerosis Protocol AC-058B202 Version 12 15 March 2022, page 149/179

Confidential

EudraCT 2009-011470-15 EDMS-ERI-206617631

to the sponsor as an SAE and the patient should be managed according to the local standard of care.

Cases of PML must be reported to the sponsor as an SAE.

If the MRI at scheduled visit shows signs atypical for MS, PML or other opportunistic infection should be considered based on the clinical signs and symptoms, MRI results, previous exposure to natalizumab or immunosuppressants, and laboratory tests including CSF analysis, if indicated. As long as there is suspicion of PML or other opportunistic infection, the study drug should be interrupted and should not be reintroduced until this suspicion has been ruled out.

B) General guidance for monitoring of subjects with opportunistic infection other than PML during treatment:

Heightened vigilance is required for opportunistic infections, with particular attention to be paid to viral infections. However, investigators and physicians following patients should also be alert to potential systemic infections caused by fungi and bacteria. In the event of opportunistic infection, the patient must discontinue the study drug and must be referred to an expert in infectious diseases for further examination and treatment.

It is important to recognize that opportunistic infections caused by the reactivation of human herpes viruses (herpes simplex viruses, varicella-zoster virus, Epstein-Barr virus, cytomegalovirus) may be associated with neurological symptoms primarily. The neurotropic herpes viruses (herpes simplex and varicella-zoster) are frequent human pathogens and their reactivation can cause serious infections of the CNS such as encephalitis and meningitis. The most frequent characteristics of these infections are of acute onset, associated with fever, headache, confusion, personality changes, and disorientation. Any suspicion of these infections must lead to immediate discontinuation of study drug treatment and to early initiation of antiviral treatment [Steiner 2007]. In the event of a suspected opportunistic infection of the CNS, FLAIR and DWI sequences may be performed and sent to MIAC. MIAC will only analyze the additional sequences selected by the site local radiologist, neuroradiologist, or neurologist with MRI expertise, upon notification for review of the investigational site. In that instance, MIAC will communicate the results of the review to the site.

Particular vigilance is required for rare and unusual neurological symptoms, as their recognition is crucial for the early diagnosis of neurotropic herpes viruses infections.

The thorough physical examination and blood tests on the routine visits should be focused on any potential signs of skin, mucosal surfaces, gastrointestinal tract, liver, hematological or other abnormality or organ dysfunction suggesting a potential opportunistic infection.

Ponesimod / ACT-128800 / JNJ-67896153 Multiple Sclerosis		EudraCT 2009-011470-15 EDMS-ERI-206617631
Protocol AC-058B202	Confidential	
Version 12		
15 March 2022, page 150/179		

Patients should be advised to be pro-active and alert in reporting any unusual neurological symptoms and any signs and symptoms indicative of systemic infections, such as fever, malaise and fatigue [Kappos 2007].

References for Appendix 3

[Kappos 2007] Kappos L, Bates D, Hartung HP, et al. Natalizumab treatment for multiple sclerosis: recommendations for patient selection and monitoring. Lancet Neurol. 2007;6:431 41.

[Kappos 2011] Kappos L, Bates D, Edan G, et al. Natalizumab treatment for multiple sclerosis: updated recommendations for patient selection and monitoring. Lancet Neurol. 2011;10:745-58

Appendix 4: Guidance for skin examination

Since the skin might be the first organ for manifestation of immunosuppression, a complete skin examination must be performed in order to distinguish normal, abnormal, and suspicious skin lesions. The skin examinations can be done by a dermatologist or by the primary investigator / treating neurologist. In the event of abnormal or suspicious findings the primary investigator / treating neurologist must refer the patient to a dermatologist for further examination, including the taking of skin biopsies if required.

In the initial examination, it is important that the patient be disrobed as completely as possible. This will minimize chances of missing important individual skin lesions. The patient should first be viewed from a distance of about 1.5 to 2 m so that the general character of the skin and the distribution of lesions can be evaluated. The presence or absence of lesions on mucosal surfaces should also be determined.

Four basic features of any skin lesion must be noted and considered in the examination of skin: the localization and distribution of lesions, the type of lesion, the shape of the individual lesion, and the arrangement of the lesion.

Special attention should be paid to nevi (moles), especially those that have recently changed, bleed, or itch. When looking at nevi, four features are essential for detection of skin cancer: Asymmetry, border irregularity, color variability, diameter >6 mm. These features or rapidly changing lesions are associated with an increased risk of malignancy.

The following descriptions of skin lesions and common dermatologic terms are provided to facilitate documentation of skin examination.

Ponesimod / ACT-128800 / JNJ-67896153 Multiple Sclerosis Protocol AC-058B202 Version 12 15 March 2022, page 152/179

Confidential

EudraCT 2009-011470-15 EDMS-ERI-206617631

EDMS-E

Descriptions of primary skin lesions

	-
Macule	A flat, colored lesion, <2 cm in diameter, not raised above the surface of the surrounding skin. A "freckle," or ephelid, is a prototype pigmented macule.
Patch	A large (>2 cm), flat lesion with a color different from the surrounding skin. This differs from a macule only in size.
Papule	A small, solid lesion, <0.5 cm in diameter, raised above the surface of the surrounding skin and hence palpable (e.g., a closed comedone, or whitehead, in acne).
Nodule	A larger (0.5 5.0 cm), firm lesion raised above the surface of the surrounding skin. This differs from a papule only in size (e.g., dermal nevus).
Tumor	A solid, raised growth >5 cm in diameter.
Plaque	A large (>1 cm), flat-topped, raised lesion; edges may either be distinct (e.g., in psoriasis) or gradually blend with surrounding skin (e.g., in eczematous dermatitis).
Vesicle	A small, fluid-filled lesion, <0.5 cm in diameter, raised above the plane of surrounding skin. Fluid is often visible, and the lesions are often translucent.
Pustule	A vesicle filled with leukocytes. Note: The presence of pustules does not necessarily signify the existence of an infection.
Bulla	A fluid-filled, raised, often translucent lesion >0.5 cm in diameter.
Cyst	A soft, raised, encapsulated lesion filled with semisolid or liquid contents.
Wheal	A raised, erythematous papule or plaque, usually representing short-lived dermal edema.
Telangiectasia	Dilated, superficial blood vessels.
·	

Ponesimod / ACT-128800 / JNJ-67896153 Multiple Sclerosis Protocol AC-058B202 Version 12 15 March 2022, page 153/179

Confidential

EudraCT 2009-011470-15 EDMS-ERI-206617631

Common dermatological terms

Lichenification	A distinctive thickening of the skin that is characterized by accentuated skin-fold markings and that feels thick on palpation.
Crust	Dried exudate of body fluids that may be either yellow (serous exudate) or red (hemorrhagic exudate).
Milia	Small, firm, white papules that are filled with keratin (and may in part resemble pustules).
Erosion	Loss of epidermis without an associated loss of dermis.
Ulcer	Loss of epidermis and at least a portion of the underlying dermis.
Excoriations	Linear, angular erosions that may be covered by crust and are caused by scratching.
Atrophy	An acquired loss of substance. In the skin, this may appear as a depression with intact epidermis (i.e., loss of dermal or subcutaneous tissue) or as sites of shiny, delicate, wrinkled lesions (i.e., epidermal atrophy).
Scar	A change in the skin secondary to trauma or inflammation. Sites may be erythematous, hypopigmented, or hypertrophic depending on their age of character. Sites on hair-bearing areas may be characterized by destruction of hair follicles.
Pruritus	A sensation that elicits the desire to scratch. Pruritus is often the predominant symptom of inflammatory skin diseases (e.g., atopic dermatitis, allergic contact dermatitis); it is also commonly associated with xerosis and aged skin.

Ponesimod / ACT-128800 / JNJ-67896153 Multiple Sclerosis Protocol AC-058B202 Version 12 15 March 2022, page 154/179

Confidential

EudraCT 2009-011470-15 EDMS-ERI-206617631

Appendix 5: Guidance for re-initiation of study drug in the event of drug interruption

If study drug intake (during uptitration or maintenance phase) is interrupted by the patient for any reason, she/he must immediately inform the primary investigator / treating neurologist.

Note that under no circumstances should a patient take more than one capsule per day during TP1 or more than one tablet per day during TP2 and TP3.

A schematic overview of the re-initiation algorithm is given in Figure 2.

Depending on the day, time, and duration of study drug interruption, the following procedures will be followed.

A) If the patient missed taking the dose in the morning:

- The dose should be taken at any time on the same day.
- Regular dosing should be resumed with the morning dose on the following day.

B) If the patient missed taking the dose for up to three consecutive days:

- Dosing should be resumed in the morning, with the same dose taken prior to study drug interruption.
- Study drug intake may be re-initiated by the patient at home.
- Patients must be instructed to contact the investigator immediately if they experience any symptoms of bradycardia (e.g., dizziness, vertigo, syncope).

C) If the patient missed taking the dose for four or more consecutive days, then the gradual uptitration scheme outlined in Table 6 (blister kit with starting dose of 2 mg) must be used:

1. Patients with cardiovascular risk factors (i.e., meeting any of the below-listed Criteria for Cardiac Monitoring at Site) will require cardiac monitoring and therefore must have their re-initiation of study drug performed at the site. On the day of the re-initiation of ponesimod, the patient must be monitored for at least 4 hours post-dose, following the cardiac assessment schedule and applying the discharge criteria as described in Appendix 2.

Criteria for Cardiac Monitoring at Site (cardiovascular risk factors):

- Sinus bradycardia HR <55 bpm;
- History or presence during the study of first or second degree Mobitz type I AV block;
- History or presence during the study of myocardial infarction or heart failure.

Ponesimod / ACT-128800 / JNJ-67896153 Multiple Sclerosis		EudraCT 2009-011470-15 EDMS-ERI-206617631
Protocol AC-058B202	Confidential	
Version 12		
15 March 2022, page 155/179		

In the event of a re-initiation, the treating neurologist may consult with the physician evaluating cardiac safety assessments and/or a cardiologist to determine the most appropriate monitoring strategy. Cardiologist advice should be sought in case of history or presence during the study of the following conditions or abnormalities:

- Atrial flutter, fibrillation or any other arrhythmias treated with anti-arrhythmic drugs;
- Unstable ischemic heart disease or cardiac decompensated failure;
- Cardiac arrest or cerebrovascular disease (e.g., transient ischemic attack, stroke);
- Mobitz Type II second degree heart block, sick sinus syndrome or sino-atrial heart block;
- Patients receiving concomitant therapy with drugs that decrease HR (e.g., betablockers, calcium channel blockers and other drugs that may decrease HR).
- 2. Patients who do not meet any of the Criteria for Cardiac Monitoring at Site (as confirmed at pre-dose ECG assessment) may either re-initiate the study drug at home after receiving a gradual uptitration blister kit with a starting dose of 2 mg from the site or re-initiate study drug at site using the blister kit with the starting dose of 2 mg and be monitored for at least 4 hours post-dose at the discretion of the investigator / treating neurologist [see Section 3.12.5.3]. Patients re-initiating study drug at home must be instructed to contact the investigator or local emergency facilities immediately if they experience any cardiac adverse effects including symptoms of potential bradycardia (e.g., dizziness, vertigo, syncope). The additional visit 14 days (±1 day) after the day of re-initiation (Day 15) [see Section 3.12.5.3] may be scheduled at the discretion of the investigator / treating neurologist.

If a blister kit with the starting dose of 2 mg is not available at the site, re-initiation should be delayed until it becomes available (temporary treatment interruption).

Ponesimod / ACT-128800 / JNJ-67896153 **Multiple Sclerosis** Protocol AC-058B202 Version 12

Confidential

EudraCT 2009-011470-15 EDMS-ERI-206617631

15 March 2022, page 156/179

Figure 2: Algorithm for management of treatment

*Patients without cardiovascular risk factors may either re-initiate study drug at home, or at site and be monitored for at least 4 hours post-dose at the discretion of the investigator / treating neurologist.

EudraCT 2009-011470-15

EDMS-ERI-206617631

Ponesimod / ACT-128800 / JNJ-67896153 Multiple Sclerosis Protocol AC-058B202 Version 12 15 March 2022, page 157/179

Confidential

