3.12.5.3 Additional visits for re-initiation or re-uptitration of study drug

As described in detail in Appendix 5, patients who miss taking the dose of study drug for 4 or more consecutive days will need to re-initiate study drug using the gradual uptitration scheme outlined in Table 6.

In such cases, there will be one or two visits:

- One visit on the day of re-initiation (Day 1) for all patients;
- An additional visit 14 days (±1 day) after the day of re-initiation (Day 15) only mandated for patients with cardiovascular risk factors [see Appendix 5] but may be scheduled for any patient at the discretion of the investigator / treating neurologist.
| Ponesimod / ACT-128800 / JNJ-67896153
Multiple Sclerosis | | EudraCT 2009-011470-15
EDMS-ERI-206617631 |
|---|--------------|--|
| Protocol AC-058B202 | Confidential | |
| Version 12 | | |
| 15 March 2022, page 109/179 | | |

The following assessments need to be done during the visits on Day 1 of re-initiation:

- SBP/DBP pre-dose and hourly (±15 min) for at least 4 hours and up to 12 hours post-dose (under the responsibility of the physician evaluating the cardiac safety assessments)¹;
- 12-lead ECG pre-dose and hourly (±15 min) for at least 4 hours and up to 12 hours post-dose (under the responsibility of the physician evaluating the cardiac safety assessments)¹;
- IVRS call and study drug dispensing²;
- Recording of changes in concomitant medication, if any;
- Recording of AEs and SAEs;
- The discharge criteria will be applied for patients undergoing cardiac monitoring. Patients may be discharged from cardiac monitoring if they meet the discharge criteria before 12 hours post-dose but no sooner than 4 hours post-dose [see Appendix 2].

For patients attending the visit 14 days after the day of re-initiation (if applicable), the following assessments need to be done:

- SBP/DBP (pre-dose);
- 12-lead ECG (pre-dose);
- IVRS call return of study drug blisters/bottles and unused medication, and dispensing of new blisters/bottles, if appropriate;
- Recording of AEs and SAEs.

These visits for when re-initiating and/or up-titrating the dose are additional unscheduled visits. The regular scheduled study visits must continue according to the original visit and assessment schedule.

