¹ All patients must have a pre-dose assessment. Only patients with cardiovascular risk factors [see Appendix 5] are required to be monitored for at least 4 hours and up to 12 hours post-dose at the study site. In this case, discharge criteria will be applied [see Appendix 2]. Patients without cardiovascular risk factors may re-initiate study drug at home or at site and be monitored for at least 4 hours post-dose at the discretion of the investigator / treating neurologist.

² Patients with cardiovascular risk factors [see Appendix 2] will receive only the uptitration kit. Patients without cardiovascular risk factors [see Appendix 2] and who re-initiated at home will receive both the uptitration kit and blisters/bottles for maintenance.

Ponesimod / ACT-128800 / JNJ-67896153 Multiple Sclerosis Protocol AC-058B202 Co Version 12 15 March 2022, page 110/179

Confidential

EudraCT 2009-011470-15 EDMS-ERI-206617631

3.12.5.4 Additional unscheduled visit 30 days after study drug interruption due to planned pregnancy with intention of study drug re-initiation post-partum

As described in Appendix 1 section D, female patients who wish to become pregnant must have a negative pregnancy test at an unscheduled visit 30 days after they interrupt the study drug before they can interrupt the contraception.

During this visit, the following assessments will be performed:

- Urine or serum pregnancy test;
- EDSS and FS assessment (performed by the evaluating neurologist);
- MRI examination;
- Assessment of methods of contraception;
- Recording of changes in concomitant medication, if any;
- Body temperature;
- Body weight;
- Physical examination;
- PFTs (FEV₁, FVC);
- 12-lead ECG and SBP/DBP (under the responsibility of the physician evaluating cardiac safety assessments or primary investigator / treating neurologist);
- Ophthalmological examination (best corrected visual acuity, low contrast visual acuity testing, visual fields, and dilated ophthalmoscopy; OCT in case of suspected clinically significant findings [e.g., macular edema]);
- Laboratory tests (central laboratory) preferably under fasting conditions: Hematology, blood chemistry, urinalysis;
- Recording of AEs and SAEs.

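### After a non-pregnancy break of four or more days, Appendix 5 mandates a monitored restart for first-degree and Mobitz I AV block, but only advises cardiology input for Mobitz II block, sick sinus syndrome and sino-atrial block (minor, cheap to close)

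*Protocol*

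**What the plan says.** Protocol Appendix 5, part C, applies when four or more consecutive daily doses are missed. It has two branches.

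- **C.1, mandatory.** Patients who meet any of the Criteria for Cardiac Monitoring at Site must restart at the site and be monitored for at least 4 hours. The criteria are sinus bradycardia below 55 bpm, myocardial infarction or heart failure, and "History or presence during the study of first or second degree Mobitz type I AV block".
- **C.2, discretionary.** Patients who meet none of those criteria, as confirmed by the pre-dose ECG, "may either re-initiate the study drug at home" or restart at the site with monitoring, as the investigator decides.

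Between the two branches is a separate list, introduced by "Cardiologist advice should be sought in case of history or presence during the study of the following conditions or abnormalities". It contains "Mobitz Type II second degree heart block, sick sinus syndrome or sino-atrial heart block". No site or monitoring requirement is attached to it.

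Section 3.12.5.3, footnote 1, confirms who must be observed after the dose: "Only patients with cardiovascular risk factors [see Appendix 5] are required to be monitored for at least 4 hours". It also says "All patients must have a pre-dose assessment". Footnote 6 to the schedule of assessments (repeated in SAP Section 6.13) likewise limits mandated post-dose readings to patients with cardiovascular risk factors. Footnote 20 does the same for the Day 15 visit.

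**The concern.** The gate to a home restart is the C.1 list alone, and the advice list is not part of it. Three conduction disorders that the protocol itself marks out for specialist input therefore carry a weaker requirement than first-degree or Mobitz I block.

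The protocol gives no reason for the difference. Section 1.3.2.4 reports sinus slowing, PR prolongation and occasional second-degree AV block after dosing. The Appendix 2 re-initiation discharge criteria treat persisting second- or third-degree block alike, with no exception by Mobitz type. Those criteria reach only some patients, however: "The discharge criteria will be applied for patients undergoing cardiac monitoring". After a Mobitz I history the post-dose check is required; after a Mobitz II history it is optional. At stake is an undetected bradyarrhythmia at home in a patient with known conduction disease.

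**Working it through.** The plan states no figure to reproduce, so the check sets the rules side by side.

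**Scope.** Section 3.6.2 allows interruptions of up to 12 weeks for reasons other than planned pregnancy. The window is 4 days to 12 × 7 = 84 days. Section 3.12.5.6 lists ECGs up to 12 hours post-dose for restarts after delivery, so those are excluded.

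**Routing one patient.** Take a patient with Mobitz II block, sick sinus syndrome or sino-atrial block, a pre-dose heart rate of at least 55 bpm, and no first-degree or Mobitz I block, infarction or heart failure.

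1. C.1 heart-rate criterion: not met.
2. C.1 AV-block criterion: not met, because it stops at Mobitz I.
3. C.1 infarction or heart-failure criterion: not met.
4. C.2 therefore applies and a home restart is allowed.
5. Section 3.11.2.1 asks for hourly ECGs on re-initiation days only where applicable, so it does not override footnote 1 of Section 3.12.5.3.

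**Required ECGs per restart** (Section 3.12.5.3 and its footnotes):

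| | C.1 | C.2 at home |
|---|---|---|
| Day 1 pre-dose | 1 | 1 |
| Day 1 post-dose, hourly to 4 hours | at least 4 | 0 |
| Day 15 pre-dose | 1 | 0 |
| Total | at least 1 + 4 + 1 = 6 | 1 |

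These counts describe the rule. They are not an event rate.

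**The rest of the advice list.** It has five entries.

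- HR-lowering drugs are already barred for the first 14 days after re-initiation (Section 3.4.4.3, Appendix 8): closed.
- Drug-treated arrhythmia is partly closed, because Appendix 1A stops study drug if a rhythm disorder needs drugs during the study.
- Unstable ischemic disease or decompensated failure is partly closed, because heart failure is a C.1 criterion.
- Cardiac arrest or cerebrovascular disease has only the advisory rule, and C.1 holds no counterpart for comparison.
- The conduction entry, with three diagnoses, is where the inconsistency lies.

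**Safeguards that already apply.**

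- The Amendment 11 rationale says no new patients will start treatment, so every restarting patient has been started before.
- SAP Section 5.4.4.1 says all subjects took 10 mg on their first day. SAP Section 5.4.5.3.1 describes hourly ECGs to 6 hours on Days 1, 8 and 15 of ponesimod. The restart kit begins at 2 mg, so that first dose was 10 / 2 = 5 times the restart dose.
- Failing the discharge criteria at 12 hours meant permanent discontinuation (Appendices 1A and 2).
- Appendix 1A also stops treatment if a rhythm disorder needs drugs or pacing.
- Section 3.3.4 requires AV blocks to be assessed for seriousness by the physician evaluating cardiac safety.

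**The case against.** The strongest reply is that the gap is barely reachable. A patient with a pre-study history has already come through a monitored start at a higher dose. An in-study episode should bring in the cardiac physician and may end treatment. What is left is a patient who stayed on drug after such an episode, then missed at least four days, had a normal enough pre-dose rate, and was sent home despite the advice to consult. Most of this stands and sets the severity. It does not explain the asymmetry: Mobitz I patients had the same monitored starts and the same pre-dose ECG, and they are still monitored on restart with the same 2 mg kit.

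A second reply is that referral to a cardiologist for an individual decision, possibly not to restart at all, is better than a fixed 4-hour rule. This is reasonable, and the fix keeps it. As written, though, nothing holds the dose until advice is given.

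Third, Section 3.3.4 makes the cardiac physician responsible for close post-dose monitoring at re-initiation visits, with no limit to C.1 patients. That is a real safeguard at the site. It does not turn a home dose into a monitored one, and footnote 1 of Section 3.12.5.3 still decides who is required to be observed.

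Fourth, Section 1.3.2.4 reports no second- or higher-degree block in the phase 3 study that used the 2 mg start. These documents do not say whether patients with the three diagnoses were in it.

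A reader might go further and infer that patients with serious conduction disease are being restarted without any cardiac check, or that the whole advice list is unprotected. The documents support neither. A pre-dose ECG is compulsory, advice should be sought, monitored on-site restart remains an option, and several of the other entries are closed or partly closed elsewhere.

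**Conclusion.** The inconsistency is real and confined to one entry with three diagnoses, in restarts after non-pregnancy interruptions. Its size in the rule is 0 required Day 1 post-dose ECGs against at least 4. Its size in patients cannot be computed: the documents give no count, and it is probably very small. The main remaining case is an in-study episode that needed neither drugs nor pacing and did not lead to discontinuation. Severity is minor, and the change is worth making because it is cheap.

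Two things cannot be seen from these documents. The cardiac exclusion criteria of the core study may already have kept such patients out. The restart diagram (Figure 2) is not shown, although its surviving footnote agrees with C.2.

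**What to change.** 1. In Appendix 5, add to the Criteria for Cardiac Monitoring at Site a history, or presence during the study, of Mobitz type II second-degree AV block, sick sinus syndrome or sino-atrial block.
2. For these three diagnoses, state that cardiologist advice must be obtained before re-initiation. Without this, the 4-hour rule could replace the individual decision on whether to restart.
3. Clerical: footnote 2 of Section 3.12.5.3 refers to "Patients without cardiovascular risk factors [see Appendix 2] and who re-initiated at home". The risk factors are defined in Appendix 5, so the reference should point there.

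Cost: Section 3.12.5.3 already has a Day 1 visit for every restarting patient. Each affected restart adds at least 4 hours of monitoring to that visit, a mandatory Day 15 visit and a cardiology consultation. The monitoring procedures and the Appendix 2 discharge criteria already exist.
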